Dosimeter Location and Measured Effective Radiation Dose in Pain Management Physicians

NCT06309407

May 7, 2024

1. Protocol Title:

Dosimeter Location and Measured Effective Radiation Dose in Pain Management Physicians

2. Objectives

The primary objective is to determine if there is a significant difference in radiation readings between dosimeters worn on the chest versus the hand of interventional pain management physicians and elucidate which dosimeter had higher readings.

The secondary objectives are to examine trends in radiation exposure in each group (chest only or chest plus hand) over the course of the study to understand if overall radiation exposure decreases over time due to changes in practice habits as a response to exposure reports. The last objective will be to track incidences of physician glove breaches in both groups to assess if wearing hand dosimeters is associated with an increased risk of the event.

3. Background

Radiation producing imaging use is ubiquitous in medicine with a wide range of imaging modalities. Of these, computed tomography (CT) and fluoroscopy are the most commonly used and are associated with some of the highest radiation exposure for patients and operators.¹⁻² This is particularly important in fields such as Interventional Pain Management where these modalities are essential to daily practice. The utilization of opioid-sparing minimally invasive techniques for low back pain and arthritis using CT and fluoroscopy has expanded over the years which has greatly increased radiation exposure among pain specialists.

Current Occupational Safety & Health Administration (OSHA) guidelines for occupational dose limitations indicate that the total maximum effective dose to the head and trunk is 12.5 mSv per calendar quarter and 187.5 mSv per quarter for the hands and feet.⁴ Complications of acute and chronic radiation exposure can include tissue reactions such as skin burns and cataracts or stochastic affects like cancer or hereditary derangements.⁵

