The use of multiple protective measures such as long needle holders, protective gloves, and lead drapes is considered the gold standard in practice and have been shown to decrease dose rates by up to 99.6% overall.^{8,14} Similarly, Hoffler et al found that, when compared to no protective measures, just the use of attenuating gloves and leaded eye protection can reduce the radiation exposure to the hands and eyes by 69.4% and 65.6% respectively.²¹ However, in a survey of 708 interventional pain physicians, 93% stated they were concerned with radiation exposure but only 63% had formal safety training and there was low overall understanding of evidence-based radiation safety practices.⁹ Therefore, better understanding of a physician's individual practices on effective radiation dose through a quality improvement study will help to close gaps in knowledge and understanding of exposure.

A dosimeter is a small device which measures the radiation the physician receives from their practice. There are several different kinds of dosimeters including the commonly worn chest monitor and others closer to the hands of the physician, such as wrist bands or rings. Carinou et al indicate that these devices are overall generally accurate at measuring the correct radiation dose but have their limitations depending on the manufacturer, scope of intended use, and material composition.¹⁵ There are currently no studies comparing dosimeter location and radiation exposure readings in pain management physicians. The effective dose detected by a single chest monitor is likely not an accurate representation of the doses received in other parts of the body in pain management physicians. There are also no published studies assessing the risk of wearing hand dosimeters in sterile procedures, such as increased frequency of glove breaches or procedure-related infections.

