The study will be performed at the Comprehensive Pain Center at Oregon Health and Science University (OHSU) and involve attending physicians and fellow physicians who consent to participate. The physicians who consent will then be randomly assigned by a computer-generated program to either the control group (chest dosimeter) or experimental group (chest plus hand dosimeter).

The control group will be assigned a chest dosimeter to wear while the experimental group will be assigned a hand and chest dosimeter. The dosimeters will be collected according to standard processing protocol every three month(s) by the designated Comprehensive Pain Center dosimeter collector. The badges will then be submitted to the vendor, Mirion, who will process the dosimeters and return an electronic report available for viewing online and at the procedure area nursing station. All study participants will also be emailed a copy of the report.

The study team will assess physician compliance with wearing the dosimeter(s) by having the procedure nurses perform a daily written audit of chest and hand dosimeter presence or absence.

Radiation measurements and compliance logs will be recorded in OHSU Microsoft Teams

Excel. We are done collecting data. We are using Microsoft Excel in Teams to input and analyze the data. Data analysis will be performed by an OHSU statistician.

Consistent with the OHSU standards for wearing hand dosimeters for sterile procedures, for each procedure the physician wearing the hand dosimeter will be required to:

- 1) Wash the hand dosimeter with one pump (2 mL) of Avaguard
- 2) Place the hand dosimeter on a bare hand
- 3) Dispense one pump (2 ml) into the palm of one hand. Dip fingertips of the opposite hand into the hand prep and work under fingernails. Spread remaining hand prep over the hand and up to just above the elbow.
- 4) Dispense one pump (2 ml) and repeat procedure with opposite hand.
- 5) Dispense final pump (2 ml) of hand prep into either hand and reapply to all aspects of both hands up to the wrists. Allow to dry. Do not use towels to dry.
- 6) Double glove both hands using sterile gloves.

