At the conclusion of each procedure, the physicians in both groups will be required to inspect their surgical gloves for any visible breaches. All breaches of one or both gloves on each hand that are recognized during or after the procedure must be reported to the study team. The physician will also indicate on which hand the hand dosimeter, if applicable, was worn.

5. Study Population

Inclusion and Exclusion Criteria

Inclusion criteria includes:

- a. Physicians actively performing fluoroscopy procedures at the OHSU Comprehensive Pain Center.

Exclusion criteria includes:

- a. Those that do not want to participate in the quality improvement project.

Number of Subjects

Of 6 attending physicians and 4 fellows that qualify for the study, we anticipate 8 participants in the study.

Vulnerable Populations

- a. Vulnerable populations are not involved in this quality improvement study.

6. Setting

The study examines radiation exposure of OHSU physicians performing their routine medical practice at the OHSU Comprehensive Pain Center Procedure Rooms 1 and 2. Hand dosimeters are currently used at OHSU in other departments. All study activities will take place at OHSU or remotely using OHSU provided secure computers, by OHSU personnel.

7. Recruitment Methods

Volunteers will be recruited through OHSU email. Consent to participate will be collected prior to the start of the study.

8. Consent Process

Participants will be de-identified in OHSU Microsoft Teams Excel. Individual consents will be obtained from Comprehensive Pain Center physicians prior to the start of the data collection period. For all procedure patients, standard procedure informed consent will be obtained.

9. Procedures

The study team will directly input data collected from dosimeters and compliance reports into OHSU Microsoft Teams Excel.

The variables that will be recorded in OHSU Microsoft Teams Excel **for each participant** will include:

- a. Group identifier – control or experimental
- b. Chest dosimeter radiation exposure reading (Total Effective Dose Equivalent in rem) for each 3-month period
- c. Hand dosimeter radiation exposure reading (Total Effective Dose Equivalent in rem) for each 3-month period
- d. Dosimeter compliance for each 3-month period (%)
- e. Report(s) and date(s) of glove breaches during the procedure

10. Data and Specimens

Handling of Data and Specimens

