No specimens will be collected for this study. OHSU Microsoft Teams Excel will be used for data collection and storage. No identifiers will be collected that could link the participant to published data. Access to data is restricted to study personnel and access to data requires OHSU ID/password authentication.

11. Sharing of Results with Subjects

The study results will be published.

12. Data and Specimen Banking

Data will not be stored for future research. Data will be retained for up to 3 years or until the study is completed and results are published.

13. Data Analysis

For the statistical analysis, to perform hypothesis testing, the statistician will use a t-test between dosimeter type and effective radiation dose.

The statistician will perform an analysis using descriptive statistics, tables, and data visualization techniques. The statistics will include median (min, max) and mean (SD) with 95% confidence intervals for continuous variables and frequencies and proportions for binary and categorical variables. The statistician will use multiple imputation to address missing data if the missing rate is more than 10%. Multiple imputation by chained equations (MICE)

is implemented assuming missing at random.

14. Privacy, Confidentiality and Data Security

Access to data during the study period is restricted to study personnel and access to data requires OHSU ID/password authentication.

Data for this project will be stored in Microsoft Teams Excel

The study team will not collect protected health information.

Standard institutional practices will be followed as described by the OHSU Information Security Directives at the following link:

<http://www.ohsu.edu/xd/about/services/integrity/policies/ipspolices-info-sec-directiv.cfm#results> to maintain the confidentiality and security of data collected in this study.

Study staff will be trained with regard to these policies. Electronic data will be stored on encrypted: computers, laptops, tablets, and iPads.

Electronic data is stored:

- On restricted drives on the OHSU network.
- OHSU Microsoft Teams Excel

Access to data is restricted to study personnel. Access to data requires OHSU ID/password authentication.

15. Risks and Benefits

a. Risk

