There is a risk of breach of confidentiality. There is no increased risk of radiation exposure to participants as they will not be asked to modify their routine medical practice in any way. There is a risk of hand dosimeters being associated with a glove breach. To address this risk, all physicians wearing hand dosimeters will be required to double glove per OHSU standards. There is no evidence of dosimeters causing increased risk to patients and standard procedure consent will be obtained per routine medical practice as is consistent with OHSU departments using hand dosimeters.

b. Potential Benefits to Participants

Identifying a discrepancy in radiation exposure between chest dosimeters and hand dosimeters that could lead to changes in provider radiation safety.

References

medical doctors. *Insights into Imaging* 12.. doi:10.1186/s13244-021-01041-2

- 4. Occupational Safety and Health Administration, (n.d.), Ionizing Radiation Standards, United States Department of Labor, <https://www.osha.gov/ionizing-radiation/standards>
- 6. Schueler BA. Operator shielding: how and why. *Tech Vasc Interv Radiol*. 2010 Sep;13(3):167-71. doi: 10.1053/j.tvir.2010.03.005. PMID: 20723831.

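### The glove-breach objective is comparative, but no between-group estimate, interval or denominator is planned, so sparse counts could look reassuring while large increases remain possible

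*Combined protocol and SAP*

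**What the plan says.** Section 2 gives the last objective as to "track incidences of physician glove breaches in both groups to assess if wearing hand dosimeters is associated with an increased risk of the event". That is a comparison between the two groups.

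Section 13 names one hypothesis test: "the statistician will use a t-test between dosimeter type and effective radiation dose". Its descriptive part promises "mean (SD) with 95% confidence intervals for continuous variables" and, for everything else, "frequencies and proportions for binary and categorical variables". Glove breaches are not mentioned there by name.

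Three other sections matter:
- Section 4 randomises physicians, not procedures, to the two groups. It has every physician inspect the gloves after each procedure, so breach observations are nested within physicians.
- Section 5 says "we anticipate 8 participants in the study". No allocation ratio is stated.
- Section 9 lists what is recorded per participant: group, chest and hand readings, compliance percentage, and breach reports with dates. The number of procedures is not on the list.

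**The concern.** The objective calls for inference, but the planned analysis is descriptive. If Section 13 is followed as written, the reader gets breach frequencies for two groups. There is no estimate of the contrast, no statement of how uncertain it is, and no recognition that about eight physicians, rather than all their procedures, carry the comparison. A per-procedure proportion could not be formed from the listed variables at all, because its denominator is not recorded.

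Of the stated objectives, this is the one that bears on sterility. Section 3 notes that "There are also no published studies assessing the risk of wearing hand dosimeters in sterile procedures", and Section 11 says the results will be published, so this may be among the first evidence on the question. With sparse data, similar small counts in the two groups could be taken as a sign of safety although a large increase would fit the same data.

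**Working it through.** The documents give no power, precision or margin figure for breaches, so there is nothing of the plan's own to reproduce. The question is what sparse results could exclude.

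**Inputs.** From the documents: 8 anticipated physicians (Section 5), randomised by physician with breaches inspected per procedure (Section 4). Assumed: a 4 v 4 split, equal procedure numbers per group, two-sided 5% level. Procedure counts and the intraclass correlation (ICC) are not given, so the values below are illustrative.

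**1. Rate ratio, clustering ignored.** With equal denominators, and given the total a + b, the hand-dosimeter count a is binomial with probability θ = RR/(1 + RR). Take the Clopper-Pearson limits for θ and convert with RR = θ/(1 − θ). For 1 v 1, the lower limit for θ is 1 − √0.975 = 0.01258 and the upper is 0.98742, so RR runs from 0.01258/0.98742 = 0.013 to 0.98742/0.01258 = 78.

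| Breaches, hand v control | 95% interval for the rate ratio |
|---|---|
| 0 v 0 | 0 to infinity |
| 1 v 1 | 0.013 to 78 |
| 2 v 2 | 0.07 to 13.8 |
| 3 v 3 | 0.13 to 7.5 |
| 5 v 5 | 0.23 to 4.3 |
| 5 v 0 | 0.92 to infinity |
| 6 v 0 | 1.18 to infinity |

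For k v 0 the two-sided exact p-value is 2 × 0.5^k: 0.063 at k = 5 and 0.031 at k = 6.

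**2. Physicians with any breach, 4 v 4.** There are C(8,4) = 70 equally likely allocations. Complete separation (4/4 v 0/4) has Fisher p = 2/70 = 0.029. The next most extreme table, 3/4 v 0/4, has p = 2 × 4/56 = 0.14. Only complete separation is below 0.05. With a 5:3 split the separated table has p = 1/56 = 0.018. If none of 4 physicians has a breach, the exact upper limit for the proportion is 1 − 0.025^(1/4) = 60.2% (70.8% for 0/3, 52.2% for 0/5).

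**3. Zero breaches per procedure, with clustering.** The upper limit is 1 − 0.025^(1/n). Replace n by n divided by the design effect, 1 + (m − 1) × ICC, where m is procedures per physician. For illustration take m = 100 and 4 physicians, so n = 400.
- ICC 0: 1 − 0.025^(1/400) = 0.92%.
- ICC 0.01: design effect 1.99, effective n = 400/1.99 = 201, limit 1.8%.
- ICC 0.02: design effect 2.98, effective n = 400/2.98 = 134, limit 2.7%.

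The limit widens by roughly the whole design effect, about 2 and 3 fold. The square root of the design effect (1.4 and 1.7) scales a standard error and would understate the widening here.

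**The case against.** The strongest defence is that this is the last objective of a quality improvement study in about eight physicians. Descriptive reporting is defensible at that size, and Section 13's list of statistics need not be exhaustive. That stands as a reason not to demand a powered test. It does not remove the gap: an objective about association needs at least an estimate with its uncertainty. Even if the interval phrase is read generously as covering proportions, no interval for the contrast between groups follows.

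A reader might infer that the sponsor will report sparse breaches as showing no added risk. No section says so; could be read that way is as far as the text goes. A reader might likewise infer from the Section 15 sentence "There is no evidence of dosimeters causing increased risk to patients" that the protocol treats absence of evidence as reassurance. It does not support that. Shortly before, the same section acknowledges that a hand dosimeter may be associated with a glove breach and describes a mitigation. The quoted sentence concerns patients and leads into consent, and the section's statement about unchanged risk refers to participants' radiation exposure.

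Sidedness is not stated. One-sided, 5 v 0 gives 0.5^5 = 0.031, so the threshold of six breaches depends on the two-sided choice. The wide intervals for equal counts do not change the message.

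The absolute bound could be tight if procedures were many and nearly independent: zero in 2000 gives 0.18%. At ICC 0.05 with 500 procedures for each of 4 physicians, it is 4.7%. An ICC cannot be estimated from zero events, so only a sensitivity range is possible. Finally, Section 4 has physicians report breaches by hand and the hand that wore the dosimeter. A within-physician comparison of hands might be possible, but the plan does not specify one.

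**Conclusion.** The concern holds. As written, Section 13 cannot answer the breach objective in Section 2: it plans no contrast, no interval and no physician-level analysis, and Section 9 records no denominator for a per-procedure rate. Equal counts of up to five per group leave a rate ratio of at least 4.3 unexcluded, before any allowance for clustering. At physician level only complete separation would be significant.

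The rate-ratio figures rest on equal denominators, and the physician-level figures mainly on a 4 v 4 split; neither needs an assumed procedure count or ICC. The zero-event limits rest on both, and are illustrations. The documents do not show how the result will be interpreted, so the risk is one of misreading. A better analysis cannot create power; it can only make the uncertainty visible.

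An interval will not cure one further problem. Sections 4 and 15 require hand-dosimeter wearers to double glove, while gloving in the control group is not described. The contrast may therefore mix the effects of dosimeter and gloving.

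**What to change.** In Section 13, add a breach analysis:
- Report breach counts by physician and by group.
- Make the main comparison at physician level: physicians with any breach, with exact 95% intervals, and a permutation comparison of physician breach counts (or rates, if denominators exist).
- If procedure counts per physician can be retrieved from existing records, also give breaches per procedure by group with an exact rate-ratio interval, labelled as ignoring clustering. Add a sensitivity range over assumed ICCs in which the effective sample size is the number of procedures divided by the design effect. If counts cannot be retrieved, say so and report the physician-level results only.
- State the largest increase not excluded. Do not conclude that risk is not increased unless the upper limit supports it.
- Note as a limitation that control-group gloving is not described while hand-dosimeter wearers must double glove.

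Section 4 says data collection is finished, so date the change and label it post hoc.

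The cost is a little more analysis work, some effort to retrieve procedure counts, and a visibly weaker safety conclusion.
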